### 7.1.3 Device Deficiency/Device Malfunction

Device deficiency is defined as an inadequacy of a medical device related to its identity, quality, durability, reliability, safety or performance, such as malfunction, misuse or use error and inadequate labeling. This includes the failure of the device to meet its performance specifications or otherwise perform as intended. Note: Performance specifications include all claims made in the labeling of the device.

A device malfunction is the failure of a device to meet its performance specifications or otherwise perform as intended, when used in accordance with the instructions for use or CIP.

## 7.2 Device Relationship

Determination of whether there is a reasonable possibility that an investigational product or device under investigation caused or contributed to an AE is to be **determined by the Investigator** and recorded on the appropriate CRF form. Determination should be based on assessment of temporal relationships, evidence of alternative etiology, medical/biologic plausibility, and patient condition (pre-existing condition).

## 7.3 Adverse Event and Device Deficiency/Device Malfunction Reporting

### 7.3.1 Adverse Event Reporting

#### General AE Reporting

Safety surveillance and reporting will be done only for enrolled subjects, and it starts when the study device is introduced into the subject's vasculature. Safety surveillance and reporting will continue through

*This confidential document is the property of Abbott and shall not be reproduced, distributed, disclosed or used without the express written consent of Abbott*

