### 3.1 Clinical Investigation Procedures Schedule

Subjects will be considered enrolled in this clinical investigation when all of the following criteria are met: Informed Consent Form (ICF) is signed, they meet all eligibility criteria and have undergone physiological indices measurement and OCT pullbacks. Enrolled subjects must follow all CIP requirements.

Data will be collected at baseline, during procedure, and post-procedure. There is no clinical follow-up in this study. The flowchart of the process is shown in **Figure 2** below.

[figure not shown]
---

Document 90465825 Virtual Flow Reserve Tech Report - Data on File at Abbott

*This confidential document is the property of Abbott and shall not be reproduced, distributed, disclosed or used without the express written consent of Abbott*

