#### 5.2 Subject Screening and Informed Consent

##### 5.2.1 Subject Screening

Potential patients presenting at the clinical sites will be fully informed about the clinical investigation, following the established Informed Consent process (described in **Section 5.2.2**). Once a duly dated and signed Informed Consent form is obtained, the clinical investigation-specific screening procedures may begin.

The following assessments are performed as part of the screening process:

- Clinical indication for angiography with potential for PCI
- Inclusion and exclusion criteria

Subjects must be screened for clinical investigation eligibility by a member of the site's clinical investigation team previously trained to the CIP, and if applicable will be entered into a site-specific screening log.

In case the subject does not meet all inclusion criteria or meets any of the exclusion criteria, the subject is considered a screening failure. The Principal Investigator or the delegated clinical investigation personnel will record the screening failure in the hospital records.

Subjects who signed an Informed Consent form and met general inclusion criteria and no exclusion criteria will participate in the clinical investigation. These patients will also be recorded in the hospital records.

Subject data will be collected following enrollment into the clinical investigation described in **Section 5.4**.

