### 5.4 Subject Enrollment

Subjects are considered enrolled in this clinical investigation after signing the ICF, met all inclusion criteria and has undergone physiological indices measurement and OCT pullbacks. If ANY of the exclusion criteria are met, the patient is excluded from the clinical investigation and cannot be enrolled.

If subjects are enrolled into the clinical investigation and are later found to have met exclusion criteria or not all inclusion criteria, these subjects will be included in the analysis population and must follow all the

*This confidential document is the property of Abbott and shall not be reproduced, distributed, disclosed or used without the express written consent of Abbott*

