## Clinical Investigation Plan

the procedure and end when the subject has left the procedure room, the subject is deceased, the subject concludes participation in the clinical investigation, or the subject withdraws from the clinical investigation, whichever occurs first. Adverse events will not be collected for screen failure subjects. All adverse event data, including deaths and device deficiency data (if applicable), will be collected throughout the time period defined above and will be reported to the Sponsor on a CRF. Additional information with regard to an adverse event should be updated within the appropriate CRF.

Unchanged, chronic, non-worsening or pre-existing conditions are not AEs and should not be reported.

An offline form will be made available to allow the investigator to report SAEs in the event the entry cannot be made in the EDC. This does not replace the EDC reporting system. All information must still be entered in the EDC system as soon as feasible.

Non-cardiac related abnormal laboratory values will not be considered AEs unless:

1. the investigator determined that the value is clinically significant,
2. the abnormal lab value required intervention, or
3. the abnormal lab value required subject withdrawal from the clinical investigation.

All adverse events will be collected on each subject through the end of the procedure.

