### SAE Reporting

The investigator should report all SAEs to the Sponsor as soon as possible but no later than outlined below.

| Clinical Site | Reporting timelines   |
|---------------|---|
| All Sites     | SAEs must be reported to the Sponsor no later than 3 calendar days from the day the site personnel became aware of the event or as per the investigative site's local requirements, if the requirement is more stringent than those outlined. |

The date the site staff became aware the event met the criteria of an SAE must be recorded in the source document. The Investigator will further report the SAE to the local IRB/EC according to the institution's IRB/EC reporting requirements.

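### The enrolled-only adverse event rule in Protocol 7.3.1 and SAP 3.2 can leave out device-exposed subjects, because enrollment is reached only after physiology and OCT

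*Protocol*

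**What the plan says.** **Who is under surveillance.** Protocol 7.3.1, General AE Reporting: "Safety surveillance and reporting will be done only for enrolled subjects, and it starts when the study device is introduced" into the vasculature. The same subsection adds: "Adverse events will not be collected for screen failure subjects". SAP 3.2 matches this and summarizes events for enrolled subjects.

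**When a subject is enrolled.** Protocol 3.1 requires a signed consent form and that "they meet all eligibility criteria and have undergone physiological indices measurement and OCT pullbacks". Section 5.4 likewise places enrollment after both measurements, and 6.2.5 requires them to have been successful. Section 5.2.2 states that signing consent is not enrollment.

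**Who is a screen failure.** Protocol 5.2.1: "In case the subject does not meet all inclusion criteria or meets any of the exclusion criteria, the subject is considered a screening failure". One of the imaging exclusions in 5.3.4 (item 4) is that the target lesion was not imaged by OCT.

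**Text that points towards wider capture.** The last line of General AE Reporting in 7.3.1 reads "All adverse events will be collected on each subject through the end of the procedure". Under SAE Reporting: "The investigator should report all SAEs to the Sponsor as soon as possible but no later than outlined below". Section 11.4 has CRF data collected for everyone who has signed consent, including those who fail the criteria at the index procedure. Section 15.5 has AEs reported to the sponsor for internal monitoring, with no enrolled qualifier. Appendix XI places an AE form step at the end of the physiology sequence, before OCT begins.

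**The concern.** AE collection and AE summary both depend on a status that a subject acquires only by getting through the two invasive measurements. A complication that ends the procedure between PressureWire insertion and the OCT pullback can therefore remove its own subject from the safety record. The reported percentage of subjects with events would then be conditional on having completed both measurements, and the cases lost would be the ones in which something went wrong early.

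At stake is the descriptive safety summary and the oversight that draws on AE reports. Protocol 3.3 gives a raised frequency of anticipated adverse device effects as an example of why an oversight committee might recommend stopping, and 15.5 relies on AE reports for safety surveillance. Sensitivity and specificity of VFR are not touched.

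**Working it through.** The plan states no figure on this point, so the check is textual.

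**Step 1. Order of events.** Protocol 6.2 and Appendix XI put the PressureWire measurements first and the OCT pullback last. Every subject therefore has a device in the coronary artery before the enrollment definition in 3.1, 5.4 or 6.2.5 can be met.

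**Step 2. Apply the rules to each place a subject can stop.**

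| Where the subject stops | Device introduced? | Enrolled? | Under 7.3.1 surveillance? | In SAP 3.2 summary? |
|---|---|---|---|---|
| Fails a criterion before any device is introduced | No | No | No | No (no device exposure is missed) |
| After PressureWire insertion, before OCT is complete | Yes | No | No | **No** |
| OCT done, screen-failed on the pullback (Appendix XI, Pre-PCI OCT, step 7) | Yes | Depends on reading of 5.4 | Depends | Depends |
| Enrolled, then rejected at core laboratory quality check (5.4, 6.6) | Yes | Yes | Yes | Yes |
| Completes both measurements and is enrolled | Yes | Yes | Yes | Yes |

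**Step 3. Second row.** No special reading is needed. The subject has not undergone OCT, so none of the three enrollment definitions is met. If the site also applies 5.3.4 item 4, the subject becomes a screening failure under 5.2.1, and 7.3.1 then bars AE collection.

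**Step 4. Third row.** Section 5.4 says that nobody who meets an exclusion can be enrolled, but also that enrolled subjects who "are later found to have met exclusion criteria or not all inclusion criteria, these subjects will be included in the analysis population". A subject found to have plaque rupture, hematoma or thrombus on the pullback is unenrolled under the first sentence and arguably enrolled under the second. Appendix XI calls this subject a screen fail, which favors the first.

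**Step 5. Is the event recorded anyway?** The texts on collection pull in two directions:

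- Against capture: the opening of General AE Reporting and the screen-failure sentence in 7.3.1, and 5.2.1, which says "Subject data will be collected following enrollment into the clinical investigation described in" Section 5.4.
- Towards capture: the last line of General AE Reporting, the SAE Reporting paragraph, 11.4, 15.5, and step 20 of Pre-PCI Physiological Indices in Appendix XI.

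Some of the second group are weaker than they look. The two 7.3.1 texts may inherit the enrolled limit that opens that section. The Appendix XI step applies only where applicable and is labelled for adverse device effects. The offline SAE form in 7.3.1 deals with failure of electronic entry, not with who is covered. The route in 7.3.2 for use before a patient ID exists covers device deficiencies and malfunctions only.

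**Step 6. Effect on the summary.** However the collection conflict is settled, SAP 3.2 is limited to enrolled subjects. An event in a second-row subject could be on the database and still not be summarized.

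**Step 7. Size.** The documents give no rate of stopping after insertion and no number exposed. The 310 in Protocol 5.6 is an enrollment target. The frequency bands in Appendix IV cannot be used instead: Table A includes thrombosis at 30 days and at one year or more, whereas AE capture here ends when the subject leaves the procedure room. No count of lost events follows from these inputs.

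**The case against.** The strongest reply has four parts.

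1. **The rule is workable as written.** Once a subject qualifies as enrolled, the window simply runs back to device introduction. That is right, and the fact that nobody is enrolled at the moment of insertion is not an error in itself. It does not help subjects who never qualify.

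2. **Other sections capture these events.** A complication that stops the procedure may well be serious, and the SAE paragraph has no enrolled qualifier. Section 11.4 names the very group at issue. This stands in part. A reader might infer that the protocol plainly discards these events; it does not. It gives sites conflicting instructions, and the clear gap is in the SAP summary.

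3. **The pullback screen failures are not lost adverse events.** Because Appendix IV Table B lists thrombus formation as an anticipated OCT event, a reader might infer that the finding which triggers the screen failure is itself the event. The documents do not show that pullback findings are device-caused. Rupture, hematoma and visible thrombus are listed as eligibility exclusions, and 7.3.1 says that pre-existing conditions are not AEs. What remains is narrower: a subject in this group may have a separate complication, and whether it is counted depends on how 5.4 is read.

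4. **Little turns on it.** No investigational device is used, VFR is computed offline, the devices are market released, and subjects are already scheduled for clinically indicated catheterization. The final CRFs, data management plan and monitoring plan are not included and may already handle these subjects. All of this stands and lowers the priority. If those documents do collect these events, the wording of 7.3.1 and SAP 3.2 would still need to agree with them.

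**Conclusion.** The point holds at lower severity. A consented subject stopped after PressureWire insertion but before OCT is complete falls outside the surveillance rule in 7.3.1 and outside the SAP 3.2 summary. Whether the event is collected at all is a conflict within the protocol, and collection is barred if the subject is classed as a screen failure. Subjects screen-failed on the pullback may also be left out, depending on 5.4.

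The size is unknown. A reader might be tempted to multiply 310 by an Appendix IV band. That would estimate events among an assumed number exposed, not events lost, and the share that stop the procedure before enrollment is not given. The conclusion assumes that 3.1, 5.4, 7.3.1 and SAP 3.2 are applied as worded and that no unseen document overrides them.

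**What to change.** **Protocol 7.3.1.** Define AE and SAE capture as every consented subject from first introduction of a study device to the end of the existing surveillance window, whether or not enrollment is later met. Limit the screen-failure exemption to failures before any device is introduced.

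**SAP 3.2.** Summarize AEs for all consented, device-exposed subjects, with enrolled subjects as a subset. Report how many were exposed but not enrolled, with reasons.

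**Reconcile** Protocol 5.2.1, 7.3.1 (including SAE Reporting), 11.4, 15.5 and the Appendix XI physiology and OCT steps with SAP 3.2. In particular, settle whether data collection starts at consent (11.4) or following enrollment (5.2.1), and which subjects the SAE paragraph covers.

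**Cost.** Wording changes in two documents; the AE form already exists. There is slightly more data entry, records are kept for some subjects who never enroll, and the reported AE rate may be higher. The co-primary analyses do not change.

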## Clinical Investigation Plan

the procedure and end when the subject has left the procedure room, the subject is deceased, the subject concludes participation in the clinical investigation, or the subject withdraws from the clinical investigation, whichever occurs first. Adverse events will not be collected for screen failure subjects. All adverse event data, including deaths and device deficiency data (if applicable), will be collected throughout the time period defined above and will be reported to the Sponsor on a CRF. Additional information with regard to an adverse event should be updated within the appropriate CRF.

Unchanged, chronic, non-worsening or pre-existing conditions are not AEs and should not be reported.

An offline form will be made available to allow the investigator to report SAEs in the event the entry cannot be made in the EDC. This does not replace the EDC reporting system. All information must still be entered in the EDC system as soon as feasible.

Non-cardiac related abnormal laboratory values will not be considered AEs unless:

1. the investigator determined that the value is clinically significant,
2. the abnormal lab value required intervention, or
3. the abnormal lab value required subject withdrawal from the clinical investigation.

All adverse events will be collected on each subject through the end of the procedure.

### SAE Reporting

The investigator should report all SAEs to the Sponsor as soon as possible but no later than outlined below.

| Clinical Site | Reporting timelines   |
|---------------|---|
| All Sites     | SAEs must be reported to the Sponsor no later than 3 calendar days from the day the site personnel became aware of the event or as per the investigative site's local requirements, if the requirement is more stringent than those outlined. |

The date the site staff became aware the event met the criteria of an SAE must be recorded in the source document. The Investigator will further report the SAE to the local IRB/EC according to the institution's IRB/EC reporting requirements.

### **7.3.2 Device Deficiency/Malfunction Reporting**

All device deficiencies/malfunctions should be reported on the appropriate CRF form.

The investigator should report all device deficiencies/malfunctions to the Sponsor as soon as possible but no later than outlined below.

| Clinical Sites | Reporting timelines |
|----------------|---------------------|
|----------------|---------------------|

*This confidential document is the property of Abbott and shall not be reproduced, distributed, disclosed or used without the express written consent of Abbott*

## Clinical Investigation Plan

|           |   |
|-----------|---|
| All Sites | Device deficiencies/malfunctions must be reported to the Sponsor no later than 3 calendar days from the day the site personnel became aware of the event or as per the investigative site's local requirements, if the requirement is more stringent than those outlined. |
|-----------|---|

The device should be returned to the Sponsor.

Device deficiencies/malfunctions should be reported to the IRB per the investigative site's local requirements.

An offline form will be made available to allow the investigator to report device deficiencies/malfunctions in the event that the entry cannot be made in the EDC system. This does not replace the EDC reporting system. All information must still be entered in the EDC system as soon as feasible.

In case a device deficiency/malfunction occurred before the patient ID has been assigned, the device deficiency should be reported to the Sponsor via the offline reporting form.

### **7.3.3 Adverse Event Reporting to Country Regulatory Authorities by the Sponsor**

The Sponsor will report SAEs and reportable device deficiencies/malfunctions to the country regulatory authority, per local requirements.

Note: Reportable device deficiencies/malfunctions include device deficiencies/malfunctions that might have led to an SAE if a) suitable action had not been taken or b) intervention had not been made or c) if circumstances had been less fortunate. These are handled under the SAE reporting system.

## **8.0 STATISTICAL CONSIDERATIONS**

The following section describes the statistical methods for the clinical investigation. Additional details on statistical analyses, including justification of clinical investigation design, sensitivity analyses, poolability analyses, subgroup analyses and analysis of descriptive endpoints, may be maintained in a separate Statistical Analysis Plan (SAP).

### **8.1 Analysis Populations**

The primary analysis population will include all subjects who have signed informed consent, met all inclusion and exclusion criteria, and have acceptable OCT pullbacks and pressure tracings for computing both the VFR and FFR indices

### **8.2 Statistical Analyses**

#### **8.2.1 Primary Endpoint(s) Analyses**

The co-primary endpoints of the study will be the sensitivity and specificity of VFR against FFR, each of which will be tested against a prespecified performance goal.

*This confidential document is the property of Abbott and shall not be reproduced, distributed, disclosed or used without the express written consent of Abbott*

## Clinical Investigation Plan

FFR with a binary cut-off of 0.80 will be used as the reference standard for comparison, and an FFR value  $\leq 0.80$  will be considered positive (ischemia-causing) and an FFR value  $> 0.80$  will be considered negative (non-ischemia-causing).

Similarly, a VFR value  $\leq 0.80$  will be considered positive (ischemia-causing) and a VFR value  $> 0.80$  will be considered negative (non-ischemia-causing).

The following 2x2 table provides diagnostic definitions of true positive (TP), false positive (FP), true negative (TN) and false negative (FN) within the context of this study.

|                 | FFR $\leq 0.80$     | FFR $> 0.80$        |
|-----------------|---------------------|---------------------|
| VFR $\leq 0.80$ | True Positive (TP)  | False Positive (FP) |
| VFR $> 0.80$    | False Negative (FN) | True Negative (TN)  |

The following sections contain these diagnostic definitions of TP, FP, FN, and TN to explain how to calculate the endpoint data.

### 8.2.1.1 Primary Endpoint: Overall Sensitivity

The first co-primary endpoint is the overall sensitivity of VFR against FFR.

#### 8.2.1.1.1 Hypothesis

[REDACTED]

[REDACTED]

[REDACTED]

[REDACTED]

#### 8.2.1.1.2 Analysis Method

The overall sensitivity of the hybrid approach will be estimated using the 2x2 contingency table comparing VFR and FFR measurements. Sensitivity is defined as the proportion of VFR positive lesions(13), in the group of FFR positive lesions, which can be expressed in the following way:

$$Sensitivity = \frac{TP}{TP + FN}$$

Where TP denotes the number of True Positives (both VFR and FFR positive) and FN denotes the number of False Negatives (VFR negative but FFR positive).

*This confidential document is the property of Abbott and shall not be reproduced, distributed, disclosed or used without the express written consent of Abbott*

## Clinical Investigation Plan

### 8.2.1.2 Primary Endpoint: Overall Specificity

The second co-primary endpoint is the overall specificity of VFR against FFR.

#### 8.2.1.2.1 Hypothesis

#### 8.2.1.2.2 Analysis Method

The overall specificity of the hybrid approach will be estimated using the 2x2 contingency table comparing VFR and FFR measurements. Specificity is defined as the proportion of VFR negative lesions in the group of FFR negative lesions(13), which can be expressed in the following way:

$$\text{Specificity} = \frac{TN}{TN + FP}$$

Where TN denotes the number of True Negatives (both VFR and FFR negatives) and FP denotes the number of False Positives (VFR positive but FFR negative).

